### **Protocol**

Study Title: Integrative Medicine for Hypermobility Spectrum Disorder (HSD) and Ehlers-Danlos (EDS) syndromes: A mixed-methods feasibility study (IMforHSDandEDS)

PI: [name]

IRB #: DH10320/PRAF

Approval Date: 03.03.21

Version: 3.0

burden, support needed, and any barriers that are encountered with the recommended dietary modifications.

- Because these measures are reported as open responses, they will be thematically summarized for representative quotes, at each time point measured.

Adherence with dietary tracking will be assessed by:

- Percentage of total days on which dietary intake was documented. Self-reporting of daily dietary intake on at least 50% of total days will be considered adherent.
- Number of weeks on which intake was self-reported at least 3 days.

For Specific Aim 3,

We will test whether the integrative medicine education intervention reduced pain and improved health-related quality of life in patients with HSD or EDS. VAS pain scores and PROMIS-29 domain scores will be summarized across participants and time points as mean (SD).

Analysis of pain and HRQoL outcomes for Aim 2 will use paired t-tests to assess mean changes unless investigation of distributions indicates a need for nonparametric testing, in which case changes will be analyzed using Wilcoxon signed-rank tests.

For Exploratory Aim 1,

Any associations between pain, HRQoL, and diet will be assessed both cross-sectionally and longitudinally over the course of treatment. Cross-sectional associations of VAS pain score, PROMIS-29 domain scores, and dietary composition measures will be analyzed using Pearson correlations (or Spearman correlations for badly non-normal data). To assess associations of longitudinal changes, we will compute changes in each measure both from baseline to 5 weeks, and from baseline to 9 weeks, and we will similarly evaluate correlations between the changes over each time period.

Cross-sectional correlations assess the association of participants' ordinary diet with pain and health-related quality of life, while correlations of changes assess the association of dietary changes, in response to the treatment recommendations, with changes in pain and HRQoL over the same time frame.

We will also assess associations between age, race, sex, baseline symptoms, and changes in outcomes at follow-up, using Pearson correlations and independent t-tests, as appropriate.

For Exploratory Aim 2,

We will summarize Patient Assessment of Chronic Illness Care (PACIC+) scores in the sample, at both baseline and study end, and mean (SD). We will also test whether the scoring changed after participating in integrative medicine intervention, using a paired t-test.

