## Protocol

Study Title: Integrative Medicine for Hypermobility Spectrum Disorder (HSD) and Ehlers-Danlos (EDS) syndromes: A mixed-methods feasibility study (IMforHSDandEDS)

PI: [name]

IRB #: DH10320/PRAF

Approval Date: 03.03.21

Version: 3.0

**B.3 Tertiary Aim:** To examine the effect of a 9-week integrative medicine intervention on overall perceived pain and quality of life in patients with Hypermobility Spectrum Disorder (HSD) or Ehlers-Danlos syndromes (EDS).

- Outcome Measures 3: Participants will complete a Visual Analog Scale for Pain (VAS Pain) and a 29-Item profile HRQoL Survey (PROMIS-29) at baseline, 5, and 9 weeks.

In order to better understand the needs of the patient population, we will also address the following exploratory aims, as far as we are able. These aims can be considered to be independent of the effects of treatment.

**B.4 Exploratory Aim 1:** To evaluate any associations between symptom severity, perceived pain, quality of life, and diet among patients with Hypermobility Spectrum Disorder (HSD) or Ehlers-Danlos syndromes (EDS).

- Participants will be given a 1-week lead-in to establish baseline food patterns before starting the prescribed food plan. Associations of dietary composition, patient-reported symptoms, as well as overall perceived pain and quality of life scores will be examined, both cross-sectionally at intake and longitudinally over the 9 weeks of the intervention.

**B.5 Exploratory Aim 2:** To assess the experiences of chronic illness care and living with chronic illness among patients with Hypermobility Spectrum Disorder (HSD) or Ehlers-Danlos syndromes (EDS).

- Outcome Measure 5: Participants will complete a 26-item survey, Patient Assessment of Chronic Illness Care (PACIC+), that evaluates areas of patient self-management within the chronic care model of healthcare. The PACIC+ ascertains attitudes regarding patient-centered care, living with chronic illness, and chronic illness care; it will be completed by participants at baseline and 9 weeks.

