## E. RESEARCH DESIGN AND METHODS

### E.1. Overview

This feasibility study will investigate the recruitment potential and retention rate among patients with Hypermobility Spectrum Disorder (HSD) or Ehlers-Danlos syndromes (EDS) participating in a 9-week integrative medicine intervention that involves a prescribed anti-inflammatory (Mediterranean) diet, as well as general behavioral and psychosocial support. The feasibility of the food plan will also be examined through participant food tracking as well as through a food plan assessment in a brief satisfaction survey. Up to 20 patients with HSD or EDS will be enrolled from the Portland Oregon area, and the in-person screening study visit and the 2 virtual follow-up visits will be conducted at or from the Healthy Living Community clinic. We will also obtain preliminary data on any effects that the 9-week integrative medicine intervention has on pain and health-related quality of life. Outcome measures will be collected at 5 and 9 weeks, with the exception of the patient assessment of care for chronic conditions (PACIC+), that will be collected at baseline and the close-out visit during week 9.

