## **E.2 Recruitment**

Participants will be recruited from a local nonprofit private medical practice in Portland, Oregon, Healthy Living Community. We will post advertisements via the Healthy Living Community email newsletter, Facebook page, as well as in the doctor's office. (See Appendices 6A and 6B)

We will also post flyers through the Portland area EDS support group, Oregon Area Ehlers-Danlos Society, as well as local physical therapy and doctor's offices that specialize in HSD and EDS in the Portland Metro area. The flyers will invite patients who believe that they have HSD or EDS and are in pain to participate in the study.

Healthy Living Community and [name] have a social media presence that may build trust among a more racially and ethnically diverse study population and help participants to research the practice and feel comfortable ahead of time. While it would greatly enhance generalizability of results, if we were able to stratify recruitment to specifically include minorities and diversify study participants, we do not consider this feasible in the current pilot study of a small local population, in which the primary barrier is to a sufficiently large sample of any demographic composition.

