### **E.3.1 Inclusion Criteria**

- Age 18-65
- Beighton score of 4 or more to confirm joint hypermobility diagnosis
- Baseline VAS Score of 1 or more
- Not currently, or already a patient of [name] and Healthy Living Community
- Ability to provide written informed consent
- Willingness to participate in 9-week integrative medicine intervention (and make dietary and lifestyle changes)
- Willingness to attend 1 in-person screening visit and 2 virtual office visits (or 3 virtual visits, if medical documentation of Beighton score can be provided in advance of enrollment, and all other criteria are met).
- Access to an electronic device for *MyFitnessPal* food-tracker use (i.e mobile device, tablet, laptop)

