### Exploratory measures:

#### *Pain Visual Analog scale (VAS), The Patient-Reported Outcomes Measurement Information System (PROMIS-29), and Dietary Adherence associations:*

#### **Protocol**

Study Title: Integrative Medicine for Hypermobility Spectrum Disorder (HSD) and Ehlers-Danlos (EDS) syndromes: A mixed-methods feasibility study (IMforHSDandEDS)

PI: [name]

IRB #: DH10320/PRAF

Approval Date: 03.03.21

Version: 3.0

- We will evaluate any associations between symptom severity, perceived pain, health-related quality of life, and dietary composition cross-sectionally and longitudinally over the course of the 9-week intervention.

*Patient Assessment of Chronic Illness Care+ scores (PACIC+) collection:*

- We will collect general perceptions and attitudes regarding the experiences of chronic illness care and living with chronic illness among patients with HSD and EDS at baseline and 9 weeks.
- The Patient Assessment of Chronic Illness Care (PACIC+) is a validated survey shown to have good reliability, internal consistency, and better psychometric characteristics than other surveys on patient satisfaction. It is designed to assess the experience and satisfaction within the chronic care model of healthcare, which often results in repeated appointments over a long time interval. It retrospectively assesses experiences of chronic illness care and living with chronic illness over the past 6 months.

*Health history and anthropometric measurements:*

- Biological information will be captured regarding the patients' previous medical health history, age, sex, and gender at the baseline screening. We will also document BMI, weight, height, and estimated energy requirement measurements at baseline. We will record patient self-reported weight at 5 and 9 weeks and track any changes that occur. Any abnormal BMI values will be monitored appropriately for safety, and any changes in these measures will be analyzed in accordance with the overall effectiveness of the diet.
- We will also document any other patient-reported symptoms that are experienced in addition to HSD or EDS throughout the 9 weeks and document any changes that occur.
- Any current pain medications or supplements that the participants are taking for pain will also be recorded.

*Beighton score: range of motion measurements*

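### Aim 3 is worded as testing whether the intervention reduced pain, but a paired test in one uncontrolled arm can show only that scores changed

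*Combined protocol and SAP*

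**What the plan says.** Section B.3 gives the tertiary aim as "To examine the effect of a 9-week integrative medicine intervention on overall perceived pain and quality of life". Section E.9, under Specific Aim 3, turns this into a test: "We will test whether the integrative medicine education intervention reduced pain and improved health-related quality of life". The analysis "will use paired t-tests to assess mean changes unless investigation of distributions indicates a need for nonparametric testing", in which case Wilcoxon signed-rank tests are used. (That sentence labels the analysis as belonging to Aim 2, although it stands under Aim 3.) No significance level or sidedness is given.

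There is one arm and no comparator. E.1 says "Up to 20 patients with HSD or EDS will be enrolled from the Portland Oregon area". VAS pain and PROMIS-29 are taken once before treatment and again at weeks 5 and 9 (B.3, E.4.1).

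On entry, E.2 says "The flyers will invite patients who believe that they have HSD or EDS and are in pain", and E.3.1 requires "Baseline VAS Score of 1 or more".

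On medication, E.6 says "Any current pain medications or supplements that the participants are taking for pain will also be recorded". The visit descriptions place this at baseline, week 5 and week 9 (E.4.4, E.4.6, E.4.8). The study requires no medication changes, and no section asks participants to keep medication constant. E.3.2 excludes people with new medications in the 90 days before entry.

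**The concern.** The wording of the aim and the method answer different questions. Whether the intervention reduced pain is a causal question. A paired comparison with baseline in one group answers whether the mean score moved. No section mentions natural course, attention effects or regression to the mean, and none limits the causal reading. One rival explanation could be partly examined with data already being collected, namely changes in analgesic use, but E.9 does not bring those data to the pain outcome.

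At stake is what the trial may conclude from Aim 3. Section F says the results could inform the healthcare community and a larger study. An attributed effect would be a poor basis for either.

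**Working it through.** The documents give no power, effect size, SD or significance level for Aim 3, so there is no stated figure to reproduce.

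**1. What the paired test addresses.** Let D be the follow-up score minus the baseline score. In a single arm,

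E(D) = intervention effect + natural course + attention or expectation + regression to the mean + effect of medication changes.

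The null hypothesis is E(D) = 0, not that the first term is 0. With no comparator there is one estimate for a sum of five terms, so the first cannot be isolated. The Wilcoxon alternative has the same limit.

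**2. Illustration.** Assumed, not from the documents: intervention effect zero, VAS mean 5, SD 2, correlation r between baseline and follow-up 0.5 to 0.7, baseline VAS at least 1, two-sided 0.05. Each setting was simulated 20,000 times, with n = 20 (full enrolment) and n = 15 (75% retention goal in B.1: 0.75 × 20 = 15). The table gives the chance of a significant fall; the nominal value is 2.5%.

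| Assumed non-specific fall (points) | n = 20 | n = 15 |
|---|---|---|
| 0 | about 3% | about 3% |
| 0.5 | 22–31% | 17–24% |
| 1.0 | 62–82% | 49–68% |
| 1.5 | 92–99% | 81–95% |

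The test responds to any mean change, whatever its cause. The documents do not say which row applies.

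**3. Regression to the mean from the written entry rule.** For selection at baseline VAS ≥ c, the expected fall is (1 − r) × SD × φ(a) / [1 − Φ(a)], with a = (c − mean)/SD.
- Mean 5, SD 2, c = 1: a = −2 and φ/(1 − Φ) = 0.0540/0.9772 = 0.055. The fall is 0.5 × 2 × 0.055 = 0.06 at r = 0.5, and 0.3 × 2 × 0.055 = 0.03 at r = 0.7.
- Mean 4: a = −1.5 and the ratio is 0.1295/0.9332 = 0.139. The fall is 0.14 at r = 0.5 and 0.08 at r = 0.7.

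The VAS rule alone is therefore close to harmless.

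**4. Medication.** The data exist at three visits. E.9 relates outcome change to age, race, sex and baseline symptoms, and medication is not on that list. The opening sentence of E.9, which summarises every measure collected, would yield at most a description. The 90-day exclusion covers the time before entry, not the nine weeks of the study.

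**5. Why these data should be tabulated and not used to drop people.** Assumed: no true change, SD of change 1.55 (2 × √[2(1 − 0.7)]), and medication increased by 50% of those who worsen by more than 1 point and by 5% of the others. P(D > 1) = 0.26, and the contribution to the mean from D > 1 is 1.55 × φ(0.645) = 0.502. The mean change in those kept is (0.50 × 0.502 − 0.95 × 0.502)/(0.50 × 0.26 + 0.95 × 0.74) = −0.226/0.833 = −0.27. Exclusion alone creates a false fall of about 0.27 points.

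**6. Comparison within E.9.** For Exploratory Aim 2 the same paired t-test is used, but the plan asks only whether PACIC+ scores changed following participation. Suitable neutral wording already exists and is not applied to pain.

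**The case against.** The best defence is proportion. This is a feasibility study, Aim 3 is tertiary, and no progression rule depends on it. The abstract, E.1 and Section F all call the effect data preliminary, and the operative sentence in E.9 speaks of mean changes. A single arm is a reasonable choice here, so the lack of a control group is not the fault. How the result will be reported is also a guess. All of this stands and limits the weight of the point. It does not remove it: preliminary describes how firm the evidence is, not what caused a change, and the Aim 3 text in E.9 lacks even that word.

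A reader might infer that recruiting people in pain builds in a large spurious fall. If self-selection acted like a VAS cut of 4 or 5 (assumed mean 5, SD 2, r 0.5 to 0.7), the expected fall would be 0.3 to 0.5 or 0.5 to 0.8 points. The documents do not support such a cut. The phrase about being in pain comes from the flyers, which are one route beside the newsletter, Facebook and office advertisements (E.2). Telephone screening, and for some a separate Beighton check, comes before the baseline VAS (E.4.2). Section C4 describes chronic pain, which need not be at a temporary peak on entry.

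A reader might also infer that the medication data go wholly unused. That is too strong, because the general summary in E.9 would cover them descriptively.

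**Conclusion.** Wrong as written. E.9 and B.3 promise a conclusion about the intervention that a paired test in one uncontrolled arm cannot deliver. This follows from the design and needs no numerical assumption.

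The size of any non-specific change in pain cannot be determined from the documents. Some regression to the mean is possible through self-selection, but the written VAS threshold contributes almost none. The simulated percentages rest on an assumed mean, SD, correlation and significance level. They show only how the test behaves and do not forecast this trial.

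The point is confined to the interpretation of Aim 3. The feasibility outcomes under Aims 1 and 2 are not affected.

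**What to change.** - Reword Aim 3 in E.9 and B.3 as estimating the within-participant change from baseline to week 5 and to week 9 in VAS pain and each PROMIS-29 domain, with 95% confidence intervals.
- State in E.9 that these changes will not be attributed to the intervention, in line with the neutral wording already used for PACIC+. Correct the Aim 2 label in the same paragraph.
- Add a table of changes in pain medication and supplements beside each participant's VAS change. Keep it descriptive, and do not exclude anyone on the basis of medication use after baseline, for the reason shown in step 5.

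Averaging a second VAS from the lead-in week into the baseline is not recommended. That week follows Visit 1, where psychosocial and behavioural support has already been given (E.4.4), so the score would precede the diet but not the intervention.

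The cost is an edit to two sections, one extra table from data already collected, and a more cautious claim. No additional visits or surveys are needed.

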## B. SPECIFIC AIMS

**B.1 Primary Aim:** To investigate the feasibility of a 9-week integrative medicine intervention, as assessed by recruitment and retention in patients with Hypermobility Spectrum Disorder (HSD) or Ehlers-Danlos syndromes (EDS).

- Outcome Measures 1: The recruitment rate will be assessed as the number of participants enrolled per month, over the duration of open recruitment. Our goal is to recruit 20 participants within a span of 4 months. Retention rate will be determined as the proportion of participants completing the mid-study or end-of-study visits, with a goal of 75% retention for each study visit.

**B.2 Secondary Aim:** To evaluate the feasibility of and adherence to a prescribed food plan as well as the feasibility of food tracking as a part of a 9-week integrative medicine intervention in patients with Hypermobility Spectrum Disorder (HSD) or Ehlers-Danlos syndromes (EDS).

- Outcome Measures 2: To assess the feasibility of the dietary recommendations, adherence will be assessed using estimated daily dietary intake recorded in *MyFitnessPal*, a food tracker app for mobile devices and computers. The participant's reported macronutrient breakdown will be compared to the prescribed food plan to calculate an adherence score. Participants will also complete a food plan satisfaction survey at baseline, 5, and 9 weeks that will examine any physical side-effects, support needed, and any barriers to adherence, including food costs. The feasibility of food tracking will be measured by adherence to the recommended use of the app. A threshold of 3 days of reporting per week (including breakfast, lunch, dinner, and snacks) for the 9-week duration of the study will be considered adherent and should provide sufficient data to assess the observance of the recommended food tracking.

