### **E.4 Participant and Procedure Schedule**

#### **E.4.1 Overview**

The study is comprised of 1 in-person screening, 2 follow-up visits, and 2 telephone or email check-in correspondences for additional support. The in-person screening and 2 virtual follow-up visits will take place at the Healthy Living Community clinic. Virtual follow-up study visits will take place via the Zoom video platform utilized by ChARM TeleHealth, a web-based and HIPAA compliant server maintained by the Healthy Living Community clinic and will occur at 5- and 9-weeks post-enrollment.

During the in-office screening, participants will have their joint mobility measured in accordance with the Brighton Scoring System to confirm that they meet the diagnostic criteria for Hypermobility Spectrum Disorder. Participants who are diagnosed using the Brighton criteria and meet other eligibility criteria will then be asked to provide informed consent (E.4.3) and enrolled in the study if willing. The Clinical Investigator will capture a complete and detailed medical history of enrolled participants, discuss family and social support, as well as prescribe a food plan. The CI will also assess the patient's current self-management strategies and provide general behavioral and psychosocial support. During the 2 follow-up visits, the Clinical Investigator will revisit these self-management strategies. As scheduling visits may be difficult at precisely 5 and 9 weeks, we will leave some flexibility for these points in time to accommodate the schedules of the Clinical investigator, the student researcher, and the participants.

At 2 and 6 weeks, the participants will be contacted by the student researcher to answer any questions, provide nutritional and psychosocial support, monitor for any adverse events, and offer solutions to any dietary challenges. Participants will also be assessed at all study visits for any adverse events.

Participants will be asked to complete pain (VAS), and health-related quality of life (PROMIS-29) instruments at baseline, 5, and 9 weeks. Adherence to the dietary recommendations, as well as the feasibility of food tracking will be obtained using *MyFitnessPal*, a food tracker app throughout the 9 weeks. A food plan satisfaction survey will be collected at 5 and 9 weeks. Participants will fill out the

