##### **Protocol**

Study Title: Integrative Medicine for Hypermobility Spectrum Disorder (HSD) and Ehlers-Danlos (EDS) syndromes: A mixed-methods feasibility study (IMforHSDandEDS)

PI: [name]

IRB #: DH10320/PRAF

Approval Date: 03.03.21

Version: 3.0

- Recruitment rate (average number of participants enrolled per month)
- Dropout rate (proportions of participants failing to complete 5 or 9-week visits)

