**Protocol**

Study Title: Integrative Medicine for Hypermobility Spectrum Disorder (HSD) and Ehlers-Danlos (EDS) syndromes: A mixed-methods feasibility study (IMforHSDandEDS)

PI: [name]

IRB #: DH10320/PRAF

Approval Date: 03.03.21

Version: 3.0

- Participants will also be assessed for any adverse events during check-in calls with the following question, "Are you experiencing any new symptoms or side-effects that you may have noticed?" We will recommend cessation of the food plan if a patient feels that any of their symptoms have been exacerbated, or if they are experiencing any new symptoms.
- Dietary alterations involving increased fats, protein, fruits, and vegetables may cause gastrointestinal distress. HSD and EDS are associated with motility issues that may result in constipation; however, adherence to a Mediterranean-style food pattern has been associated with improved gastrointestinal symptoms. We will monitor these symptoms closely and recommend cessation of the food plan if a patient is experiencing significant digestive distress.

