### **E.9 Statistical Analysis**

All measures collected in the study, including baseline characteristics and outcome measures, will be summarized using mean and SD (biomarkers, anthropometrics), median and IQR (Beighton score), or percentage within each level, for categorical variables. All statistical analyses will be performed at the National University of Natural Medicine.

For Specific Aim 1,

Feasibility of the 9-week integrative medicine intervention will be measured through recruitment and retention at each follow-up visit. Recruitment rate will be presented as the mean number of participants enrolled per month, with enrolment ceasing either after 4 months, or when n=20 participants have been enrolled. Retention will be calculated as the percentage of enrolled participants from whom follow-up data is obtained, at either the 5-week or 9-week visit.

For Specific Aim 2,

Adherence to the recommended diet will be assessed in different ways and tracked by macronutrient levels and dietary composition. In particular, we will assess:

- Percentage of days on which the diet recommendations were met; in order to satisfy this requirement, macronutrient distribution must meet all of the following:
  - Carbohydrates between 40-50%
  - Protein between 15-20%
  - Fat between 25-30 %
- Number of weeks in which recommendations were met at least 5 days;
- Whether recommendations were met on at least 75% of total days (Y/N)
- Mean of weekly adherence scores calculated over the 9-week study period.

Percentage of days and weeks adherent will be summarized across participants as median/IQR/range. We will also present the percentage of participants who met the threshold of 75% days adherent.

Feasibility of the 9-week integrative medicine intervention will also be measured through self-reported food plan satisfaction surveys that assess any negative outcomes, overall cost-prohibitiveness or

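### Aim 3's paired tests leave out anyone without a week-9 score, which can bias week-9 change toward improvement; a three-visit mixed model reduces this but does not always remove it

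*Combined protocol and SAP*

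**What the plan says.** **Analysis.** Under Specific Aim 3, E.9 says the pain and HRQoL analysis "will use paired t-tests to assess mean changes" unless distributions point to a nonparametric test, "in which case changes will be analyzed using Wilcoxon signed-rank tests". The sentence names Aim 2, but it stands under Aim 3 and concerns Aim 3's outcomes, so it is read here as Aim 3. E.9 does not say which visits are compared. It gives no analysis set, missing-data method or sensitivity analysis for VAS or PROMIS-29. The only missing-data rule in the protocol concerns food-tracking weeks (E.5, MyFitnessPal).

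**Schedule.** E.4.1: "Participants will be asked to complete pain (VAS), and health-related quality of life (PROMIS-29) instruments at baseline, 5, and 9 weeks".

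**Size and loss.** B.1: "Our goal is to recruit 20 participants within a span of 4 months", and retention is planned "with a goal of 75% retention for each study visit". E.9 closes recruitment "with enrolment ceasing either after 4 months, or when n=20 participants have been enrolled".

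**Dropout and stopping.** E.6 defines "Dropout rate (proportions of participants failing to complete 5 or 9-week visits", that is, by missed visits. Separately, the adverse-event part of E.6 says staff will "recommend cessation of the food plan if a patient feels that any of their symptoms have been exacerbated". For check-in calls E.6 adds new symptoms as a trigger, and E.6 and E.8 add significant digestive distress. No section says that a participant who stops the food plan leaves follow-up. None says expressly that VAS and PROMIS-29 are still collected from that participant.

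**The concern.** A paired t-test or signed-rank test on baseline-to-week-9 change uses only participants seen at both visits. Someone who scores worse at week 5 and then misses week 9 adds nothing to the week-9 result, although the week-5 score says something about where that person was heading. The plan treats a loss of a quarter at each visit as success, so this is an expected situation.

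Loss may be related to outcome. A participant who feels worse is advised to stop the central component of the intervention and may then have less reason to attend. If so, the week-9 mean change describes those who did well enough to stay. Sections A and F present the pain and quality-of-life results as preliminary observations on effect, and F looks ahead to a larger study, so an optimistic figure could be carried forward.

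**Working it through.** The plan states no SD, correlation, effect size, alpha or power for Aim 3, so there is no figure to reproduce. Sample size and retention come from B.1. Everything else below is an assumption: VAS SD 2 points, true change 0, 25% of participants without a week-9 score. Negative values mean false improvement.

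**1. Pairs left.** 0.75 × 20 = 15 pairs; 5 participants are absent from the week-9 test.

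**2. Bias identity.** With a fraction d lost,

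bias = d × (mean change in those retained − mean change in those lost).

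At d = 0.25, if those lost do 1, 2 or 3 points worse than those retained, the bias is 0.25 × (−1) = −0.25, 0.25 × (−2) = −0.50, or 0.25 × (−3) = −0.75. If the groups do not differ it is 0. If improvers are the ones lost, the sign reverses.

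**3. Large-sample size of the bias.** All loss occurs after week 5, with log-odds rising by 1 to 2 per SD of week-5 change.

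- Equal correlations of 0.5 to 0.8: complete-pair bias −0.14 to −0.32.
- Adjacent visits more strongly correlated (for example baseline–week 5 0.6, baseline–week 9 0.5, week 5–week 9 0.8): −0.33 to −0.50.
- Three-visit likelihood estimate in the same cases: about 0.

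If loss is instead driven by the unseen week-9 change, complete-pair bias is −0.27 to −0.64 and the likelihood estimate is still off by −0.17 to −0.46. I re-ran these large-sample cases and obtained the same ranges to within 0.01.

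**4. Trials of 20.** 4,000 simulated trials per row, with log-odds 1.5 per 2 points of worsening. The likelihood column is the point estimate from a three-visit model with unstructured covariance. The last column is the paired t-test's false-positive rate at a nominal two-sided 5%.

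| Loss depends on | Correlation | Bias, complete pairs | Bias, likelihood | False positives |
|---|---|---|---|---|
| nothing | 0.5 | 0.00 | 0.00 | 5.0% |
| nothing | 0.7 | 0.00 | 0.00 | 5.1% |
| observed week-5 worsening | 0.5 | −0.272 | 0.005 | 8.4% |
| observed week-5 worsening | 0.7 | −0.180 | 0.002 | 7.2% |
| unseen week-9 worsening | 0.5 | −0.560 | −0.404 | 20.1% |
| unseen week-9 worsening | 0.7 | −0.360 | −0.268 | 14.0% |
| worsening before week 5, only baseline seen | 0.5 | −0.290 | −0.155 | 7.3% |
| worsening before week 5, only baseline seen | 0.7 | −0.191 | −0.141 | 7.2% |

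Share of the bias left by the likelihood model in the last four rows: 0.404/0.560 = 72%, 0.268/0.360 = 74%, 0.155/0.290 = 53%, 0.141/0.191 = 74%.

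**5. Precision.** With random loss the likelihood SE is slightly smaller: 0.505 against 0.521 (3%) and 0.400 against 0.404 (1%). With loss driven by week-5 worsening it is larger: 0.541/0.509 = 1.06 and 0.419/0.399 = 1.05. In a separate simulation with a log-odds slope of 2 the ratios were 0.62/0.53 = 1.17 and 0.44/0.40 = 1.10. Precision is therefore not the reason to change the method.

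**The case against.** A reader might infer that the plan sends worsening participants out of the study. The documents do not support that. The advice is to stop the food plan, whereas dropout in E.6 is a missed visit. The psychosocial component does not depend on the diet, follow-up visits are virtual and free of charge, and E.6 says existing conditions will be checked throughout the 9 weeks. Someone who stops the diet and attends stays in the paired test. The triggers are also any symptom or digestive distress rather than VAS pain, so diet-related loss need not bias pain change at all. This stands: the mechanism is plausible but inferred.

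A reader might also infer that a mixed model cures the problem. It does so only if loss depends on scores already observed. The check-ins at weeks 2 and 6 make the other cases realistic: a person lost after week 2 has only a baseline, and worsening reported at week 6 is not in the week-5 score. This stands too, and is why the model alone is not a sufficient remedy.

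Three further points hold in part. A participant lost after week 5 still counts in any baseline-to-week-5 test. Under week-5-driven loss the biases are below one standard error (0.272 against 0.509, 0.180 against 0.399), though under unseen worsening they are about one or above (0.560 against 0.462, 0.360 against 0.364). Finally, E.9 reports retention, so the amount of loss will be visible; which participants were lost, and how they were doing, will not.

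**Conclusion.** The concern holds in conditional form. The paired tests exclude anyone without the follow-up value, the plan accepts 25% loss at each visit, and nothing in E.9 deals with missing VAS or PROMIS-29 scores. If worsening makes a missed week-9 visit more likely, mean change at week 9 is biased toward improvement by about 0.14 to 0.50 VAS points, given SD 2, correlations of 0.5 to 0.8, and 25% loss after week 5 driven by week-5 worsening. The bias is zero if loss is unrelated to outcome. The documents fix neither its direction nor its size.

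A three-visit likelihood model was less biased than complete pairs in every informative case examined and no worse under random loss. It removes the bias only under missing at random. When worsening is unseen, a substantial part remains, often more than half.

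Aim 3 is tertiary in a single-arm study of up to 20 people. No model makes the mean change causal, and the conclusions on recruitment and retention are unaffected. The change is worth making because it is cheap and uses data already collected.

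**What to change.** In E.9, under Specific Aim 3:

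- Analyse VAS pain and each PROMIS-29 domain with one repeated-measures mixed model over baseline, week 5 and week 9: visit as a three-level factor, unstructured covariance, REML, and a small-sample degrees-of-freedom correction. Include every participant with a baseline value.
- Report week-5 and week-9 change with 95% confidence intervals.
- Keep the paired t-test or Wilcoxon test as a sensitivity analysis.
- Add a sensitivity analysis that assigns worse outcomes to those lost, over a stated range, and report the reasons for loss by visit.

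In E.4 or E.6, state that VAS and PROMIS-29 are still collected at weeks 5 and 9 from participants who stop the food plan. This concerns data collection only and leaves the stopping advice as it is.

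**Cost.** Some rewording and a little more analysis, with no added visits or instruments. The main analysis then rests on missing at random, and under strong informative loss its standard error may be up to about 20% larger (17% in the worst case simulated).
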